 - Fever $\ge 39.0^{\circ}\text{C} (\ge 102.1^{\circ}\text{F})$.
 - Redness or swelling at the injection site measuring greater than 10 cm (>20 measuring device units).

- Severe pain at the injection site.
- Any severe systemic event.
- Ask the participant to contact the site staff or investigator if the participant experiences acute chest pain, shortness of breath, or palpitations (see Section 10.10.8.6.7).
- Ask the participant to contact the site staff or investigator if a medically attended event (eg, doctor's visit, emergency room visit) or hospitalization occurs.
- Ask the participant to contact the site staff or investigator (this could be via the COVID-19 illness e-diary) immediately if he or she experiences any respiratory symptoms as detailed in Section 10.10.8.6.4.1.
- Schedule an appointment for the participant to return for the next study visit.
- Remind the participant to bring the reactogenicity e-diary to the next visit.
- Complete the source documents.
- The investigator or an authorized designee completes the CRFs and an unblinded dispenser/administrator updates the study intervention accountability records.
- The investigator or appropriately qualified designee reviews the reactogenicity e-diary data online following vaccination to evaluate participant compliance and as part of the ongoing safety review. Daily review is optimal during the active diary period.

10.10.8.6.1.2. Visit 402 – 1-Month Follow-Up Visit (After Substudy D Vaccination 1) (28 to 35 Days After Visit 401)

- Record AEs as described in Section 8.3.
- Review the participant's reactogenicity e-diary data. Collect stop dates of any reactogenicity e-diary events ongoing on the last day that the reactogenicity e-diary was completed and record stop dates in the CRF if required.
- Record nonstudy vaccinations as described in Section 6.8.
- Record details of any of the prohibited medications specified in Section 6.8.1 received by the participant if required for his or her clinical care.
- For participants who are HIV-positive, record the latest CD4 count and HIV viral load.
- Discuss contraceptive use as described in Section 5.3.
- Collect a blood sample for immunogenicity testing.

• If the participant is part of the group for description of cell-mediated immune response (select sites only), collect a blood sample (approximately 120 mL) for PBMC isolation.

Only if the participant is to receive a second dose of BNT162b2 OMI (Substudy D Vaccination 2):

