- Ask the participant to contact the site staff or investigator if a medically attended event (eg, doctor's visit, emergency room visit) or hospitalization occurs.
- Ask the participant to contact the site staff or investigator (this could be via the COVID-19 illness e-diary) immediately if the participant experiences any respiratory symptoms as detailed in Section 10.10.8.6.4.1.
- Schedule an appointment for the participant to return for the next study visit.
- Complete the source documents.
- The investigator or an authorized designee completes the CRFs.
- The investigator or appropriately qualified designee reviews the reactogenicity e-diary data online following vaccination to evaluate participant compliance and as part of the ongoing safety review. Daily review is optimal during the active diary period.

10.10.8.6.1.3. Visit 403 – 1-Month Follow-Up Visit (After Substudy D Vaccination 2) (28 to 35 Days After Visit 402): Only for Those Participants Who Receive Substudy D Vaccination 2

- Record AEs as described in Section 8.3.
- Review the participant's reactogenicity e-diary data. Collect stop dates of any reactogenicity e-diary events ongoing on the last day that the reactogenicity e-diary was completed and record stop dates in the CRF if required.
- Record nonstudy vaccinations as described in Section 6.8.
- Record details of any of the prohibited medications specified in Section 6.8.1 received by the participant if required for his or her clinical care.
- Discuss contraceptive use as described in Section 5.3.

- Collect a blood sample for immunogenicity testing.
- If the participant is part of the group for description of cell-mediated immune response (select sites only), collect a blood sample (approximately 120 mL) for PBMC isolation.
- Ask the participant to contact the site staff or investigator if a medically attended event (eg, doctor's visit, emergency room visit) or hospitalization occurs.
- Ask the participant to contact the site staff or investigator (this could be via the COVID-19 illness e-diary) immediately if the participant experiences any respiratory symptoms as detailed in Section 10.10.8.6.4.1.
- Ensure the participant has a self-swab kit.
- Schedule an appointment for the participant to return for the next study visit.
- Complete the source documents.
- The investigator or an authorized designee completes the CRFs.

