- Schedule an appointment for the participant to return for the next study visit.
- Complete the source documents.
- The investigator or an authorized designee completes the CRFs.

Only if the participant consents to receive a dose of BNT162b2 OMI (Substudy D Vaccination 2):

NOTE: Voluntary, written, study-specific informed consent will be obtained from the participant before the participant receives a dose of BNT162b2 OMI at Visit 404. Each signature on the ICD must be personally dated by the signatory. The investigator or his or her designee will also sign the ICD. A copy of the signed and dated ICD must be given to the participant. The source data must reflect that the informed consent was obtained before the participant receives a dose of BNT162b2 OMI.

NOTE: Participants who do not provide consent to receive a dose of BNT162b2 OMI at Visit 404 will remain on the single-dose visit schedule.

- Perform urine pregnancy test on WOCBP as described in Section 8.2.5.
- Discuss contraceptive use as described in Section 5.3.
- Measure the participant's body temperature.

- Ensure and document that all of the inclusion criteria and none of the exclusion criteria are met.
 - Note: a positive SARS-CoV-2 NAAT result without symptoms or a COVID-19 diagnosis (based on signs/symptoms only or signs/symptoms and a positive SARS-CoV-2 NAAT result) should not result in discontinuation of study intervention. Please see Section 7.1.
- Ensure that the participant meets none of the temporary delay criteria as described in Section 5.5.
- Obtain a nasal (midturbinate) swab (collected by site staff).
- Unblinded site staff member(s) will dispense/administer 1 dose of BNT162b2 OMI into the deltoid muscle of the preferably nondominant arm. Please refer to the IP manual for further instruction on this process.
- Blinded site staff must observe the participant for at least 30 minutes after study intervention administration for any acute reactions. Record any acute reactions (including time of onset) in the participant's source documents and on the AE page of the CRF, and on an SAE form as applicable.
- Ensure the participant has a measuring device to measure local reactions at the injection site and a thermometer for recording daily temperatures.
- Ensure the participant has a self-swab kit.

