- Review the participant's reactogenicity e-diary data. Collect stop dates of any reactogenicity e-diary events ongoing on the last day that the reactogenicity e-diary was completed and record stop dates in the CRF if required.
- Record nonstudy vaccinations as described in Section 6.8.
- Record details of any of the prohibited medications specified in Section 6.8.1 received by the participant if required for his or her clinical care.
- Discuss contraceptive use as described in Section 5.3.
- Collect a blood sample for immunogenicity testing.
- If the participant is part of the group for description of cell-mediated immune response (select sites only), collect a blood sample (approximately 120 mL) for PBMC isolation.
- Ask the participant to contact the site staff or investigator if the participant experiences acute chest pain, shortness of breath, or palpitations (see Section 10.10.8.6.7).

- Ask the participant to contact the site staff or investigator if a medically attended event (eg, doctor's visit, emergency room visit) or hospitalization occurs.
- Ask the participant to contact the site staff or investigator (this could be via the COVID-19 illness e-diary) immediately if the participant experiences any respiratory symptoms as detailed in Section 10.10.8.6.4.1.
- Ensure the participant has a self-swab kit.
- Schedule an appointment for the participant to return for the next study visit.
- Complete the source documents.
- The investigator or an authorized designee completes the CRFs.

10.10.8.6.2.5. Visit 404b – 1-Month Follow-Up Visit (After Substudy D Vaccination 2) (28 to 35 Days After Visit 404): Only for Those Participants Who Receive Substudy D Vaccination 2

- Record AEs as described in Section 8.3.
- Review the participant's reactogenicity e-diary data. Collect stop dates of any reactogenicity e-diary events ongoing on the last day that the reactogenicity e-diary was completed and record stop dates in the CRF if required.
- Record nonstudy vaccinations as described in Section 6.8.
- Record details of any of the prohibited medications specified in Section 6.8.1 received by the participant if required for his or her clinical care.
- For participants who are HIV-positive, record the latest CD4 count and HIV viral load.
- Discuss contraceptive use as described in Section 5.3.
- Collect a blood sample for immunogenicity testing.

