Note: a positive SARS-CoV-2 NAAT result without symptoms or a COVID-19 diagnosis (based on signs/symptoms only or signs/symptoms and a positive SARS-CoV-2 NAAT result) should not result in discontinuation of study intervention. Please see Section 7.1.

- Measure the participant's body temperature.
- Ensure that the participant meets none of the temporary delay criteria as described in Section 10.10.5.5.
- Obtain a nasal (midturbinate) swab (collected by site staff).
- Obtain the participant's vaccine vial allocation using the IRT system.
- Site staff member(s) will dispense/administer 1 dose of BNT162b2 OMI into the deltoid muscle of the preferably nondominant arm. Please refer to the IP manual for further instruction on this process.
- Site staff must observe the participant for at least 30 minutes after study intervention administration for any acute reactions. Record any acute reactions (including time of onset) in the participant's source documents and on the AE page of the CRF, and on an SAE form as applicable.
- Ensure the participant has a measuring device to measure local reactions at the injection site and a thermometer for recording daily temperatures.
- Ensure the participant remains comfortable with the chosen e-diary platform, confirm instructions on e-diary completion, and ask the participant to complete the reactogenicity e-diary from Day 1 through Day 7, with Day 1 being the day of vaccination.
- Ask the participant to contact the site staff or investigator immediately if the participant experiences any of the following from Day 1 through Day 7 after vaccination (where Day 1 is the day of vaccination) to determine if an unscheduled reactogenicity visit is required:
 - Fever $\ge 39.0^{\circ}\text{C} (\ge 102.1^{\circ}\text{F})$.
 - Redness or swelling at the injection site measuring greater than 10 cm (>20 measuring device units).
 - Severe pain at the injection site.
 - Any severe systemic event.
- Ask the participant to contact the site staff or investigator if the participant experiences acute chest pain, shortness of breath, or palpitations (see Section 10.10.8.6.7).
- Ask the participant to contact the site staff or investigator if a medically attended event (eg, doctor's visit, emergency room visit) or hospitalization occurs.

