- The investigator or an authorized designee completes the CRFs.
- Record any AEs that occur within the 48 hours after the blood draw as described in Section 8.3.

10.10.8.6.3.6. Visit 506 – 6-Month Follow-Up Visit (After Vaccination 2) (150 to 199 Days After Visit 502) and Administration of Vaccination 3

- Vaccination 3 may be administered as early as 5 months (150 days) after Vaccination 2.
- Record AEs as described in Section 8.3.
- Collect a blood sample for immunogenicity testing.
- If the participant is part of the group for description of cell-mediated immune response (select sites only), collect a blood sample (approximately 120 mL) for PBMC isolation.
- Record nonstudy vaccinations as described in Section 6.8.
- Record details of any of the prohibited medications specified in Section 6.8.1 received by the participant if required for his or her clinical care.
- For participants who are HIV-positive, record the latest CD4 count and HIV viral load.

- Discuss contraceptive use as described in Section 5.3.
- Perform urine pregnancy test on WOCBP as described in Section 8.2.5.
- Measure the participant's body temperature.
- Ensure and document that all of the inclusion criteria and none of the exclusion criteria are met.

Note: a positive SARS-CoV-2 NAAT result without symptoms or a COVID-19 diagnosis (based on signs/symptoms only or signs/symptoms and a positive SARS-CoV-2 NAAT result) should not result in discontinuation of study intervention. Please see Section 7.1.

- Ensure that the participant meets none of the temporary delay criteria as described in Section 5.5.
- Obtain a nasal (midturbinate) swab (collected by site staff).
- Obtain the participant's vaccine vial allocation using the IRT system.
- Unblinded site staff member(s) will dispense/administer 1 dose of study intervention into the deltoid muscle of the preferably nondominant arm. Please refer to the IP manual for further instruction on this process. Vaccination 3 may be administered as early as 5 months (150 days) after Vaccination 2.
- Blinded site staff must observe the participant for at least 30 minutes after study intervention administration for any acute reactions. Record any acute reactions (including time of onset) in the participant's source documents and on the AE page of the CRF, and on an SAE form as applicable.
- Ensure the participant has a measuring device to measure local reactions at the injection site and a thermometer for recording daily temperatures.

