- Remind the participant of the e-diary technologies available for this study (see Section 10.10.8.6.5). Provide instructions on e-diary completion and ask the participant to complete the reactogenicity e-diary from Day 1 through Day 7, with Day 1 being the day of vaccination, and, if utilized, the COVID-19 illness e-diary (to be completed if the participant is diagnosed with COVID-19 or has possible new or increased symptoms, and when he/she receives a reminder, at least weekly).
- Ask the participant to contact the site staff or investigator immediately if he or she experiences any of the following from Day 1 through Day 7 after vaccination (where Day 1 is the day of vaccination) to determine if an unscheduled reactogenicity visit is required (see Section 10.8.8.3.7):
 - Fever $\ge 39.0^{\circ}\text{C} (\ge 102.1^{\circ}\text{F})$.

- Redness or swelling at the injection site measuring greater than 10 cm (>20 measuring device units).
- Severe pain at the injection site.
- Any severe systemic event.
- Ask the participant to contact the site staff or investigator if a medically attended event (eg, doctor's visit, emergency room visit) or hospitalization occurs.
- Ask the participant to contact the site staff or investigator (this could be via the COVID-19 illness e-diary) immediately if he or she experiences any respiratory symptoms as detailed in Section 10.10.8.6.4.1.
- Ensure the participant has a self-swab kit.
- Schedule an appointment for the participant to return for the next study visit.
- Complete the source documents.
- The investigator or an authorized designee completes the CRFs.
- Record any AEs that occur within the 48 hours after the blood draw as described in Section 8.3.

10.10.8.6.3.7. Visit 507 – 1-Month Follow-Up Visit (After Vaccination 3) (28 to 35 Days After Visit 506)

- Record AEs as described in Section 8.3.
- Review the participant's reactogenicity e-diary data. Collect stop dates of any reactogenicity e-diary events ongoing on the last day that the reactogenicity e-diary was completed and record stop dates in the CRF if required.
- Record nonstudy vaccinations as described in Section 6.8.
- Record details of any of the prohibited medications specified in Section 6.8.1 received by the participant if required for his or her clinical care.
- For participants who are HIV-positive, record the latest CD4 count and HIV viral load.
- Discuss contraceptive use as described in Section 5.3.

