10.10.8.6.7. Additional Procedures for Monitoring of Potential Myocarditis or Pericarditis

Any study participant who reports acute chest pain, shortness of breath, palpitations, or any other symptom(s) that might be indicative of myocarditis or pericarditis within 4 weeks after a study vaccination should be specifically evaluated, preferably by a cardiologist, for possible myocarditis or pericarditis. In addition to a clinical evaluation, the following should be performed:

- ECG and
- Measurement of the troponin level

If myocarditis or pericarditis is suspected based upon the initial evaluation, the following should also be performed:

- Cardiac echocardiogram and/or
- Cardiac magnetic resonance study

Details of the symptoms reported, and results of the investigations performed, will be recorded in the CRF.

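### Substudy D: the request to report chest pain, breathlessness or palpitations is missing from the dosing lists at Visits 402, 404 and 506, though the 4-week cardiac evaluation rule applies after every dose

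*Protocol*

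**What the plan says.** Section 10.10.8.6.7 states that a participant who reports suggestive symptoms "within 4 weeks after a study vaccination should be specifically evaluated, preferably by a cardiologist, for possible myocarditis or pericarditis". An ECG and a troponin measurement follow, with echocardiography and/or cardiac magnetic resonance if suspicion remains. The rule attaches to any study dose, not only the first.

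The request that starts this process is a bullet in the visit lists. Visit 502, a second-dose visit, has it: "Ask the participant to contact the site staff or investigator if the participant experiences acute chest pain, shortness of breath, or palpitations". So do Visit 401 in both Cohort 1 and Cohort 2, and Visit 501.

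Three other lists also give a dose:

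- Visit 402 (Section 10.10.8.6.1.2), for Group 2, in the block opening "Only if the participant is to receive a second dose of BNT162b2 OMI (Substudy D Vaccination 2".
- Visit 404 for Cohort 2 (Section 10.10.8.6.2.3), in the block opening "Only if the participant consents to receive a dose of BNT162b2 OMI (Substudy D Vaccination 2".
- Visit 506 (Section 10.10.8.6.3.6), whose heading includes "150 to 199 Days After Visit 502) and Administration of Vaccination 3".

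None of the three contains the bullet. Each passes from the Day 1 to Day 7 reactogenicity items straight to medically attended events. In Cohort 2 the request reappears at Visit 404a: "if the participant experiences acute chest pain, shortness of breath, or palpitations (see Section 10.10.8.6.7".

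**The concern.** The work-up depends on a participant's report, so the request to report is its practical trigger. Each dose opens a new 4-week period, yet the request is made at some doses and not at others.

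The protocol does not appear to rely on one standing instruction. Visit 502 repeats the request although Visit 501 made it only 19 to 23 days before. Visit 506 falls 150 to 199 days after Visit 502, and Visit 404 falls 85 to 123 days after Visit 401 for those dosed there. The need for a reminder is greater at both.

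The Amendment 8 entry in Section 10.13 suggests how the Visit 402 gap arose: the bullet was removed there because the visit lay outside the reporting period. That is true of the first dose. For Group 2, Visit 402 is also Day 1 of the period after the second dose. This is background only; the point rests on the current text.

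At stake is prompt detection of a recognised risk after doses that fall under the primary safety objective. No effect on an immunogenicity comparison is claimed.

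**Working it through.** The plan gives no figure to reproduce. The check compares all seven Substudy D dosing lists and then counts doses from Section 10.10.4.1 and Table 10.

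| Dosing list | Maximum planned doses | Request in list? | Next listed visit after the dose |
|---|---|---|---|
| 401, Cohort 1 | 615 | Yes | 402, day 28 to 35 |
| 402, Group 2 | 205 | **No** | 403, day 28 to 35: no request |
| 401, Cohort 2 | 600 | Yes | 402, day 28 to 35 |
| 404, Cohort 2 (optional) | 600 | **No** | 404a, day 5 to 9: request present |
| 501, Cohort 3 | 205 | Yes | 502, day 19 to 23: request present |
| 502, Cohort 3 | 205 | Yes | 503 (cell-mediated subset only), then 504 |
| 506, Cohort 3 | 205 | **No** | 507, day 28 to 35: no request |

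**Total doses.** 615 + 205 + 600 + 600 + (3 × 205) = 2635.

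**Doses given under a list without the request.** 205 + 600 + 205 = 1010, and 1010 / 2635 = 38.3%. Cross-check: 615 + 600 + 205 + 205 = 1625 with the request, and 1625 + 1010 = 2635.

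**Doses with no listed re-prompt inside 28 days.** The next list after Visit 402 is Visit 403 ("28 to 35 Days After Visit 402): Only for Those Participants Who Receive Substudy D Vaccination 2"), and after Visit 506 it is Visit 507 ("1-Month Follow-Up Visit (After Vaccination 3) (28 to 35 Days After Visit 506"). Both fall on or after day 28 and neither contains the request. So 205 + 205 = 410, and 410 / 2635 = 15.6%.

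**Visit 404.** With the request back at day 5 to 9, 28 − 9 = 19 to 28 − 5 = 23 days of the window remain.

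**Uptake.** The Visit 404 and Visit 506 doses both need the participant's consent, so these counts are maxima. With no Visit 404 doses the affected share is 410 / 2035 = 20.1%. With no Visit 404 or Visit 506 doses it is 205 / 1830 = 11.2%. The share affected therefore runs from about 11% to 38%.

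**What the other prompts cover.** COVID-19 surveillance (Section 10.10.8.6.4) lists shortness of breath, but not chest pain or palpitations. The severe-systemic-event item stops at Day 7, and the solicited systemic events in Section 10.10.3 include no cardiac symptom. The medically-attended-event item works only if care is sought. AEs are recorded at Visits 403 and 507, but at 28 to 35 days that is late for a timely ECG or troponin.

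**The case against.** The strongest reply is that nobody goes uninstructed. Everyone dosed at Visits 402, 404 or 506 was told at Visit 401, or at Visits 501 and 502, to report these symptoms, and that instruction has no end date, whereas the reactogenicity instruction is limited to 7 days. Section 10.10.8.6.7 binds whatever the visit lists say. The medically-attended-event and respiratory-symptom prompts remain at all three visits. Most of the 1010 doses are Visit 404 doses, where the request returns within about a week. The Substudy D schedule of activities and master Sections 2.3, 8.2 and 8.3 are outside the part of the protocol available for this review and may carry an instruction covering every dose. By Amendment 11 some Cohort 1 and 2 participants had already completed the 6-month visit, so many Visit 402 and 404 doses may already have been given.

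All of this stands as a limit on the weight of the point: the gap is in repeating a request, not in the duty to evaluate. It does not remove the inconsistency. Visit 502 shows that the protocol repeats the request at a later dose even after a short interval, and Visit 404a shows that a request after the Visit 404 dose was intended. After the Visit 402 and Visit 506 doses, no listed scheduled visit makes it within the 4 weeks.

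**Conclusion.** The point holds. Three of seven Substudy D dosing lists omit a safety request that the other four make. They cover up to 1010 of 2635 planned doses (38%) if every optional dose is accepted. The firmer figure is the Visit 402 and Visit 506 doses: up to 410 (16%), with no listed re-prompt before day 28. For the Visit 404 doses the effect is a delay of 5 to 9 days.

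The practical loss is narrow: chest pain or palpitations, without medical care sought, in someone who was given the instruction at another dose. No missed event has been estimated, and no planned comparison is shown to be biased. The conclusion assumes that the sections not available contain no instruction applying at every dose; if they do, the effect is smaller, but the visit lists still disagree. It is worth correcting because it concerns a cardiac safety signal and the remedy is very cheap.

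**What to change.** Copy the existing bullet, with its cross-reference to Section 10.10.8.6.7, into the vaccination blocks at Visit 402 (Group 2), Visit 404 (Cohort 2) and Visit 506 (Cohort 3), and send sites a notice. Visits 403 and 507 need no change, since they fall at or past the end of the window.

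The cost is one bullet in three lists and one site communication, with no new procedure, visit or staff. If dosing at any of these visits is already complete, the study report should say instead that the request to report cardiac symptoms differed by dose.
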